2. BACKGROUND

2.1 Unresectable Carcinoma of the Pancreas

Cancers involving the upper gastrointestinal tract often present at advanced stages. While surgical resection offers some potential for long-term disease control, few patients present when disease can be addressed with a successful resection. As such, many patients with this disease have an overall survival that is less than one year after diagnosis. Because these cancers may progress both locally and distantly, and cause significant symptoms, patients are candidates to receive a combination of local Radiation Therapy (RT) and systemic chemotherapy. For patients with non-metastatic pancreatic cancer, data support the use of 5-Fluorouracil and RT as a means to favorably impact overall survival (Moertel, 1981). Typically, RT is given concurrently with radiosensitizing chemotherapy using conventional fraction sizes (1.8-2 Gy/fraction), over 5-6 weeks of treatment. Fewer data are available to support the use of RT for carcinoma of ampulla. However, it is known that these cancers are aggressive and have high rates of recurrence after surgical resection (Carter, 2008). In the unresectable setting, whether patients present with locally advanced or metastatic disease, lack of treatment may result in local symptoms including pain, gastrointestinal or biliary obstruction, bleeding, or perforation. For patients who are candidates to receive therapy, RT may be a useful adjunct to systemic chemotherapy to palliate patients of these symptoms (Boz, 2001).

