3. PATIENT SELECTION

3.1 Eligibility Criteria

- 3.1.1 Patients must have histologically confirmed, unresected cancer of the pancreas or ampulla. The cancer may include any invasive histology (e.g. adenocarcinoma, neuroendocrine carcinoma). Patients with lymph node involvement or distant metastasis may be included if it is felt that local control of the primary site of disease would help reduce, or prevent the development of, local symptoms.
- 3.1.2 Patients must have measurable radiographic disease. Patients with previous complete resection are only eligible if there is measurable radiographic disease which is clearly felt to represent locally recurrent disease.
- 3.1.3 Patients may receive any number of cycles of chemotherapy prior to treatment with SBRT, but not within 2 weeks of the first fraction of RT. Patients are not required to receive any chemotherapy to be eligible for study enrollment.
- 3.1.4 Age ≥ 18 years. The effects of this therapy are unstudied in the pediatric population.
- 3.1.5 ECOG performance status ≤ 2 (Karnofsky $\geq 60\%$, see Appendix A).
- 3.1.6 Life expectancy of greater than 3 months.
- 3.1.7 Patients must have normal organ and marrow function as defined below:
 - Absolute neutrophil count (ANC) $\geq 1,800$ cells/mm³
 - Platelets $\geq 100,000$ cells/mm³
 - Hemoglobin ≥ 8.0 g/dl
 - Creatinine $\leq 2 \times$ institutional upper limit of normal
 - total bilirubin $\leq 2.5 \times$ institutional upper limit of normal
 - AST(SGOT) or ALT(SGPT) $\leq 2.5 \times$ institutional upper limit of normal
- 3.1.8 Ability to understand and the willingness to sign a written informed consent document.

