- Grade 3+ cholecystitis (interventional radiology or operative intervention indicated)

These severe, late toxicities will be evaluated between 1 and 12 months of therapy. There is no minimum follow-up time after RT start required for patient data to contribute enough follow-up for toxicities of interest.

Enrollment of 12 additional toxicity-evaluable patients at the MTD will provide a cohort of 18 patients at the putative MTD. If six or fewer of the 18 patients experience a toxicity of interest during the evaluation period, the combination will be considered tolerable. If 7 or more patients experience a toxicity of interest, the study committee will suspend accrual and determine whether further dose modifications are needed; the protocol will be amended accordingly. If the true probability of DLT at the MTD is 50%, the combination will be identified as too toxic with probability 0.88. If the true probability of DLT at the MTD is 25%, the combination will be identified as having an acceptable toxicity profile with probability 0.86.

Management associated with the above adverse events is outlined in Section 7.

Dose escalation will proceed within each cohort according to the following scheme. Dose-limiting toxicity (DLT) is defined above.

Number of Patients with DLT at a Given Dose Level	Escalation Decision Rule
0 out of 3	Enter 3 patients at the next dose level
≥ 2	Dose escalation will be stopped. This dose level will be declared the maximally administered dose (highest dose administered). Three (3) additional patients will be entered at the next lowest dose level if only 3 patients were treated previously at that dose.
1 out of 3	Enter at least 3 more patients at this dose level. 
 • If 0 of these 3 patients experience DLT, proceed to the next dose level. • If 1 or more of this group suffer DLT, then dose escalation is stopped, and this dose is declared the maximally administered dose. Three (3) additional patients will be entered at the next lowest dose level if only 3 patients were treated previously at that dose.
≤ 1 out of 6 at highest dose level below the maximally administered dose	This is generally the recommended phase 2 dose. At least 6 patients must be entered at the recommended phase 2 dose.

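### The 0.88 and 0.86 for the 7-of-18 late-toxicity rule assume complete observation that Section 4.3 does not require, and the plan does not say which risk they describe when patients die

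*Combined protocol and SAP*

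**What the plan says.** The rule is in Section 4.3. The cohort is defined first: "Enrollment of 12 additional toxicity-evaluable patients at the MTD will provide a cohort of 18 patients at the putative MTD". The two outcomes follow: "If six or fewer of the 18 patients experience a toxicity of interest during the evaluation period, the combination will be considered tolerable", and "If 7 or more patients experience a toxicity of interest, the study committee will suspend accrual". The window runs from month 1 to month 12.

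On follow-up the section states: "There is no minimum follow-up time after RT start required for patient data to contribute enough follow-up for toxicities of interest". For acute DLT, by contrast, it asks for at least 3 weeks of the 28-day period.

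Two operating characteristics are given. "If the true probability of DLT at the MTD is 50%, the combination will be identified as too toxic with probability 0.88"; at a true 25%, "the combination will be identified as having an acceptable toxicity profile with probability 0.86".

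Other sections bear on this:

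- Section 8.1.1 treats all patients as evaluable for toxicity from their first RT treatment.
- Section 4.6 ends follow-up at 12 months or death.
- Section 4.7 keeps patients who are removed from study under observation for toxicity.
- Section 9.3 plans Kaplan-Meier only for local control, and Section 9.2 says only that late toxicities will be documented.
- On prognosis, Section 2.1 says that "many patients with this disease have an overall survival that is less than one year after diagnosis", and Section 3.1.6 requires only "Life expectancy of greater than 3 months".

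**The concern.** A fixed denominator of 18, an 11-month window and no follow-up requirement together mean that time nobody observed is treated as time without toxicity. The plan has no exclusion, censoring or replacement rule for late toxicity that would prevent this. The 3-week minimum does not help, because it is over before the late window opens.

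Incomplete follow-up can only remove events from the count, so any resulting error favours calling the dose tolerable. That call is the safety conclusion of the expansion cohort. The population is one in which the protocol itself expects many early deaths, so the two probabilities quoted in support of the rule need a stated condition and a stated target.

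**Working it through.** **Inputs.** From Section 4.3: n = 18, flag at 7 or more events, accept at 6 or fewer, true risks of 50% and 25%, window of months 1 to 12. The documents give no death or loss rate, so those below are assumptions shown as ranges.

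**1. The plan's own figures.** For X ~ Binomial(18, p):

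- P(X ≥ 7 | p = 0.50) = 1 − (1 + 18 + 153 + 816 + 3060 + 8568 + 18564)/2^18 = 1 − 31180/262144 = 0.881. The plan states 0.88.
- P(X ≤ 6 | p = 0.25) = 0.861. The plan states 0.86.

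Both reproduce, with each of the 18 patients carrying the full risk.

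**2. Patients lost alive.** Suppose m of the 18 have no late observation and count as event-free. The boundary stays at 7, but only 18 − m patients can supply events, so X ~ Binomial(18 − m, p):

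| m | flags a 50% risk | accepts a 25% risk |
|---|---|---|
| 0 | 0.881 | 0.861 |
| 1 | 0.834 | 0.893 |
| 2 | 0.773 | 0.920 |
| 3 | 0.696 | 0.943 |
| 4 | 0.605 | 0.962 |

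This needs no survival model. A patient lost partway through the window costs less than one with no late observation. If on average 90% or 80% of the risk is observable (p = 0.45 or 0.40, n = 18), the flag probability is 0.774 or 0.626.

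**3. Deaths without toxicity.** There are two readings of the 50%.

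- *Crude risk*: the chance that a treated patient has a late toxicity by month 12, with death able to come first. The count out of 18 is then binomial with p = 0.50 whatever the mortality, and 0.88 holds.
- *Risk in patients who live to 12 months.* Assume a constant toxicity hazard λ = ln 2/11 per month over months 1 to 12, and independent exponential death from RT start with hazard μ = ln 2/median. The chance of an observed event is p = exp(−μ) × λ/(λ + μ) × (1 − exp(−11(λ + μ))). For a 12-month median, p = 0.944 × 0.522 × 0.735 = 0.362.

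| assumed median survival from RT start (months) | observable risk p | P(X ≥ 7), n = 18 |
|---|---|---|
| 6 | 0.270 | 0.19 |
| 9 | 0.327 | 0.37 |
| 12 | 0.362 | 0.49 |
| 18 | 0.402 | 0.63 |
| 24 | 0.424 | 0.70 |

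At a true 25% under the same reading, acceptance rises above 0.86. With a 12-month median it is 0.97.

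**The case against.** The strongest reply concerns deaths. The rule asks whether patients experience a toxicity during the evaluation period, and a patient who dies of cancer at month 2 did not. If the true probability is the crude risk, 0.88 is correct however many patients die. This stands. A reader might infer from the second table that the plan's 0.88 is simply wrong, or that deaths are shown to bias the rule. The documents do not support that, because they never say which risk is meant. Those figures apply to one reading only and rest on assumed survival.

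Other replies have partial force:

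- Section 4.7 keeps removed patients under observation, so loss alive may be small. This limits how many are unobserved, not what each one does to the calculation.
- The survival statement in Section 2.1 runs from diagnosis, not RT start, and neuroendocrine carcinoma is eligible. Medians beyond 12 months are therefore shown too.
- RT-related deaths can be Grade 5 events, so not every death hides a toxicity.
- The follow-up sentence could mean only that a late event counts whenever it occurs, and Section 4.3 does speak of toxicity-evaluable patients. That early leavers remain as event-free is inferred from the fixed 18 and Section 8.1.1; the plan does not say it in words. No other denominator is defined, however.
- The rule is not the only safeguard. Section 6 provides weekly toxicity review and immediate reporting of Grade 4 and 5 events.

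**Conclusion.** The point holds in two parts.

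For patients lost alive, the crude count leans towards tolerable, and the stated 0.88 is not secured: 0.83 with one unobserved patient and 0.60 with four, at a 50% risk and an unchanged boundary. The direction is certain. The size depends on how many are lost, which the documents do not indicate.

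For deaths without toxicity, the defect is an undefined target. Under the crude-risk reading nothing is lost. Under the other reading the flag probability is 0.19 to 0.70 for assumed medians of 6 to 24 months, given constant hazard and death independent of toxicity.

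The binomial arithmetic itself is correct. What is missing is the condition under which it applies. This should be put right before the tolerability conclusion is drawn; it does not invalidate the design.

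**What to change.** In Section 4.3, with a matching entry in Section 9:

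1. Remove the no-minimum-follow-up sentence as the basis for the denominator of the tolerability conclusion.
2. State which risk the 50% and 25% refer to. The two sentences giving the probabilities say DLT while the rule counts late toxicities of interest; reconcile the terms.
3. State that 0.88 and 0.86 hold only with complete observation to 12 months (or to death, under the crude-risk reading). Give the flag probabilities for a range of incomplete follow-up, as in the tables above.
4. Leave 7 events as the trigger for suspending accrual.
5. Base the final tolerability statement on the 12-month cumulative incidence of late toxicity, with death as a competing event and patients lost alive censored at their last toxicity assessment. Add a Kaplan-Meier estimate that also censors deaths as a sensitivity analysis, and give confidence intervals for both. If nobody is lost alive, the cumulative incidence equals events/18, so the analysis departs from the crude proportion only where follow-up is missing.

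A suspension rule that weights each event-free patient by the share of the window observed, and acts when events over summed weights reach 7/18, is not recommended. Without a minimum number of patients, a single early event gives 1/1. It also treats death as censoring, so it targets a different quantity from item 5. If all toxicity falls in months 1 to 6, it accepts a 25% risk with only about 0.73 to 0.82, even at one final look.

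Cost: protocol wording and a short analysis from visit and toxicity dates that the Section 7 calendar already collects, with no extra patients. The quoted detection probability will look less favourable.

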Statistical Methods: A 3+3 dose escalation design will be used. The maximum tolerated dose will be exceeded if 2 or more patients out of 6 (or a third or more) experience a dose limiting toxicity (DLT) at that dose. The dose immediately below will be recommended for further study. DLTs are defined as any acute toxicity of Grade 4 nausea, Grade 4 skin toxicity, Grade 3+ liver toxicity (metabolic or ascites), or Grade 3+ enteritis. Severe late toxicities of interest (occurring beyond the 4 week period of evaluation and up to 12 months after RT) will include any Grade 3+ gastrointestinal toxicity (such as small bowel ulcer, stricture, perforation, bleed, liver damage, pancreatitis, or cholecystitis). If the rate of any severe late toxicity of interest exceeds 25% (i.e., 7 or more patients in the expanded cohort of 18 treated at the MTD), the study committee will suspend accrual and determine whether further dose modifications are needed; the protocol will be amended accordingly.

TABLE OF CONTENTS

SCHEMA	ii
1. OBJECTIVES	1
1.1. Primary Objectives	1
1.2. Secondary Objectives	1
2. BACKGROUND	1
2.1 Unresectable carcinoma of the pancreas	1
2.2 Rationale	1
3. PATIENT SELECTION	3
3.1 Eligibility Criteria	3
3.2 Exclusion Criteria	3
3.3 Inclusion of Women and Minorities	4
4. TREATMENT PLAN	4
4.1 Radiation Therapy dose escalation	4
4.2 Measuring Health Related Quality of Life	4
4.3 Definition of Dose-Limiting Toxicity	5
4.4 General Concomitant Medication and Supportive Care Guidelines	7
4.5 Duration of Therapy	7
4.6 Duration of Follow Up	8
4.7 Criteria for Removal from Study	8
5. RADIATION THERAPY GUIDELINES	8
5.1 Treatment related planning procedures	8
5.2 RT planning parameters	8
5.3 RT Treatment	10
6. ADVERSE EVENTS	10
7. STUDY CALENDAR	133
8. MEASUREMENT OF EFFECT	144
8.1 Antitumor Effect – Solid Tumors	144
9. STATISTICAL CONSIDERATIONS	155
9.1 Study Design/Endpoints	155
9.2 Sample Size/Accrual Rate	166
9.3 Analysis of Secondary Endpoints	166
10. CONFIDENTIALITY	166
10.1 Patient confidentiality issue	17
REFERENCES	18
APPENDIX A	20
APPENDIX B	21
APPENDIX C	22
APPENDIX D	23

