4.3 Definition of Dose-Limiting Toxicity

The evaluation period of acute toxicity will be defined by the period of 28 days following the first fraction of RT. Dose Limiting Toxicity (DLT) will be defined according to Common Toxicity Criteria version 3.0 (See Appendix B) and includes the following acute toxicities:

- Grade 4 nausea (life-threatening consequences)
- Grade 4 skin toxicity (necrosis or ulceration of full thickness dermis, spontaneous bleeding from involved site)
- Grade 3+ liver toxicity including symptomatic ascites requiring invasive procedure, or total bilirubin $>3 \times$ ULN, or AST $>5 \times$ ULN, or ALT $>5 \times$ ULN that persists until day 28, and is attributable to radiation therapy.
- Grade 3+ enteritis (abdominal pain, fever, change in bowel habits with ileus, peritoneal signs) that is attributable to radiation therapy.

Patients must have a minimum of 3 weeks of follow-up after RT start for patient data to contribute enough follow-up for consideration of dose-limiting toxicity. However, any DLT that occurs with shorter follow-up will count towards the dose escalation rules. In addition, any grade 5 toxicity (i.e., death) considered possibly, probably or likely related to RT will be considered a DLT.

Any late toxicity that occurs beyond the 4 week period of evaluation will be closely followed and documented as a toxicity of interest. Included are the following severe late toxicities of RT:

- Grade 3+ gastrointestinal ulcer, fistula, stricture, or perforation (symptomatic and severely altered GI function, IV fluids or TPN ≥ 24 hrs, intervention indicated)
- Grade 3+ gastrointestinal mucositis (confluent ulcerations or pseudomembranes, bleeding with minor trauma)
- Grade 3+ gastrointestinal bleed (transfusion, interventional radiology or endoscopic or operative intervention)
- Grade 3+ gastrointestinal necrosis (inability to aliment adequately by GI tract, interventional radiology, intervention indicated)
- Grade 3+ liver toxicity including symptomatic ascites requiring invasive procedure, or total bilirubin $>3 \times$ ULN, or AST $>5 \times$ ULN, or ALT $>5 \times$ ULN, or asterixis, that is attributable to radiation therapy.

- Grade 3+ enteritis (abdominal pain, fever, change in bowel habits with ileus, peritoneal signs) that is attributable to radiation therapy.
- Grade 3+ pancreatitis (interventional radiology or operative intervention indicated)

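### The 0.88 and 0.86 are stated for the probability of DLT, but the 7-of-18 rule counts only late toxicities, and acute DLTs in the expansion enter no written numerical rule

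*Combined protocol and SAP*

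**What the plan says.** Section 4.3 separates two kinds of event by time.

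- **DLT (acute).** "The evaluation period of acute toxicity will be defined by the period of 28 days following the first fraction of RT". The listed DLTs are acute toxicities, plus any grade 5 toxicity at least possibly related to RT. Their stated use is the escalation table, which works with cohorts of 3 to 6.
- **Toxicity of interest (late).** "Any late toxicity that occurs beyond the 4 week period of evaluation will be closely followed and documented as a toxicity of interest". The window is given as "These severe, late toxicities will be evaluated between 1 and 12 months of therapy". Section 6 draws the same line at 28 days.

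The expansion follows: "Enrollment of 12 additional toxicity-evaluable patients at the MTD will provide a cohort of 18 patients at the putative MTD". Its rule counts the late event: "If six or fewer of the 18 patients experience a toxicity of interest during the evaluation period, the combination will be considered tolerable", and "If 7 or more patients experience a toxicity of interest, the study committee will suspend accrual". The Schema words the same 7-of-18 rule for late events only, beginning "If the rate of any severe late toxicity of interest exceeds 25" (percent). Section 9.2 also mentions only late toxicities when it refers to modifying enrollment.

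The properties of the rule are then given for the other event: "If the true probability of DLT at the MTD is 50%, the combination will be identified as too toxic with probability 0.88". A matching sentence gives 0.86 for an acceptable profile at a DLT probability of 25%.

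Section 9.1 and the Schema say the MTD is exceeded at 2 or more DLTs in 6, or one third or more. Section 6 provides weekly safety review, and immediate reporting of life-threatening grade 4 and all fatal toxicities.

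**The concern.** The rule and its stated properties refer to different events within one paragraph. A reader of section 4.3 would take it that a dose with a 50% DLT rate is flagged in the 18-patient cohort with probability 0.88. The rule that is supposed to do this never counts a DLT.

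The primary objective is the MTD, which is defined by acute DLTs. By the time the expansion opens, that judgement rests on 6 patients. The 12 further patients would triple the acute information at the chosen dose, but the protocol does not say what number of DLTs among them, or among all 18, leads to any action.

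**Working it through.** **Inputs from the documents.** 18 patients at the MTD, of whom 6 come from escalation and 12 from expansion; suspension at 7 or more of 18 (4.3); at most 1 DLT in 6 required at the recommended dose (4.3 table); the one-third criterion (9.1).

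**Assumptions.** Independent patients with common rates, and acute and late events independent within a patient. The 10% late rate is illustrative; section 2.2 cites about 10% grade 3+ toxicity, but for another regimen. The acute rates have no source in the documents, so a range is shown.

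**1. The stated figures.** With X ~ Bin(18, p):
- P(X ≥ 7 | p = 0.50) = 0.881, stated as 0.88.
- P(X ≤ 6 | p = 0.25) = 1 − 0.139 = 0.861, stated as 0.86.

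Both reproduce. Here p is the probability of whatever event the 7-of-18 rule counts, which is a late toxicity of interest.

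**2. The rule as written.** The DLT rate does not enter. P(X ≥ 7 of 18) is 0.001 at a late rate of 10%, 0.051 at 20%, 0.139 at 25% and 0.881 at 50%. At a 50% DLT rate one expects 12 × 0.50 = 6 DLTs in the expansion, yet the suspension probability is 0.001 if the late rate is 10%, or 0.139 if it is 25%.

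**3. If the rule did count DLTs.** The expansion opens only after at most 1 DLT in 6, so the relevant probability is conditional. With b(x) = P(Bin(6, p) = x):

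P(≥ k of 18 | ≤ 1 of 6) = [b(0)·P(Bin(12, p) ≥ k) + b(1)·P(Bin(12, p) ≥ k − 1)] / [b(0) + b(1)]

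- p = 0.50, k = 7: (0.0156 × 0.387 + 0.0938 × 0.613) / 0.1094 = 0.58.
- p = 0.25, k = 7: (0.178 × 0.0143 + 0.356 × 0.0544) / 0.534 = 0.041, so acceptance is 0.96.

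**4. A dose that passes the 3+3 by chance.** At p = 0.40, P(≤ 1 of 6) = 0.0467 + 0.1866 = 0.233. Given that:
- 6 or more of 18 have a DLT: (0.0467 × 0.335 + 0.1866 × 0.562) / 0.233 = 0.52.
- 7 or more: (0.0467 × 0.158 + 0.1866 × 0.335) / 0.233 = 0.30.

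**5. A combined count.** Count each patient once for an acute DLT or a late toxicity. Each expansion patient has an event with probability 1 − (1 − acute)(1 − late), which is 1 − 0.60 × 0.90 = 0.46 at 40% and 10%. Among the first 6, at most 1 has a DLT and each of the others has a late event with probability 0.10. Summing over these cases gives 0.57 for 7 or more of 18.

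| Acute DLT rate | P(≤ 1 of 6) | ≥ 6 DLTs of 18, given ≤ 1 of 6 | ≥ 7 DLTs of 18, given ≤ 1 of 6 | Combined ≥ 7 of 18, given ≤ 1 of 6 (late 10%) | Rule as written (late 10%) |
|---|---|---|---|---|---|
| 25% | 0.53 | 0.12 | 0.04 | 0.22 | 0.001 |
| 33% | 0.36 | 0.31 | 0.14 | 0.39 | 0.001 |
| 40% | 0.23 | 0.52 | 0.30 | 0.57 | 0.001 |
| 50% | 0.11 | 0.78 | 0.58 | 0.78 | 0.001 |

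**The case against.** **The label is a slip.** The Schema ties the same rule to a 25% late-toxicity rate, so DLT in the two probability sentences may simply stand for toxicity of interest. This is plausible, and it would make 0.88 and 0.86 correct for late events. The wording would still have to change, and acute DLTs in the expansion would still have no boundary.

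**The one-third criterion covers the 18.** In 9.1 and the Schema it is not expressly limited to 6 patients, and 4.3 calls the dose only the putative MTD. But the criterion stands in the description of the 3+3 design and is not linked to the expansion. Applied to 18 it gives a boundary of 6, with P(X ≥ 6) = 0.95 at 50% and P(X ≤ 5) = 0.72 at 25%. Those are not the stated figures.

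**Safety review exists.** This stands. A reader might infer that acute toxicity in the expansion is ignored, or that a too-toxic dose cannot be caught. The documents do not support that: toxicities are assessed at scheduled visits and reviewed weekly, and grade 4 and 5 events are reported at once. What is missing is a numerical boundary, and discretionary review cannot supply the 0.88.

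**The illustration can be inflated.** This also stands. Without conditioning on the 3+3 result, the combined count at 40% and 10% flags with probability 0.80; the relevant figure is 0.57. The 40% is an assumption. Independence is doubtful, because grade 3+ liver toxicity and enteritis appear on both the acute and late lists, and some acute events may persist into the late window.

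**Six patients is ordinary 3+3 practice.** True, and no fault is found with that. The point concerns the rule for the 18.

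**Conclusion.** The concern holds in this form: the 7-of-18 rule does not have the stated 0.88 and 0.86 for DLT, because it does not count DLTs, and acute DLTs in the 12 expansion patients enter no written numerical rule. The mismatch follows from the text alone and needs no assumption. The arithmetic behind the two figures is correct; the event named is not the one counted.

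The size depends on assumed rates. With a 10% late rate independent of DLT, the written rule suspends with probability 0.001 whatever the DLT rate. A combined 7-of-18 count, given at most 1 DLT in 6, would suspend with probability 0.22 to 0.78 for acute rates of 25% to 50%. The documents do not support the stronger inference that such a dose would go unnoticed.

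**What to change.** Reconcile the Schema and sections 4.3, 9.1 and 9.2 so that all state which events the 18-patient rule counts. Section 9.2 should also point to 4.3, where the rule stands, instead of 5.2. Let acute DLTs in all 18 patients enter a stated boundary, for example by counting each patient once for an acute DLT or a late toxicity of interest.

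Attach the probabilities to the event actually counted:
- At 7 of 18, the unconditional figures remain 0.88 at 50% and 0.86 at 25%.
- If only DLTs are counted, the figures given at most 1 DLT in the first 6 are 0.58 and 0.96. For a combined count the conditional figures depend on the acute/late split, which should be stated.
- If the sponsor prefers to align with the one-third criterion (6 of 18), the unconditional figures become 0.95 and 0.72; 0.88 and 0.86 cannot be kept.

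**Cost.** No new data are needed, but a combined boundary is a change of design as well as wording, and suspension becomes somewhat more frequent. At assumed rates of 10% acute and 15% late, the combined rate is 1 − 0.90 × 0.85 = 0.235. The probability of suspension then rises from 0.01 (late only, 7 of 18) to 0.11 at 7 of 18 (0.09 given at most 1 DLT in 6), or to 0.23 at 6 of 18 (0.20 conditional). If the sponsor keeps a late-only rule, the minimum is to correct the event named in the two probability sentences and to say how DLTs in the expansion are handled.
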